- Formulation: CYRAMZA[®] (ramucirumab) is a concentrate for solution for infusion supplied in 10 mL or 50 mL single-use vial. Each vial contains either 100 mg ramucirumab in 10 mL (10 mg/mL) or 500 mg ramucirumab in 50 mL (10 mg/mL).
- Route of administration: IV infusion
- Dose regimen: Ramucirumab will be administered as an 8 mg/kg IV infusion administered over 1 hour on Day 1 of every 2 week cycle.

Tusamitamab ravtansine

- Formulation: tusamitamab ravtansine is supplied as a 25 mL extractable volume of concentrate for solution for infusion of 125 mg contained in a 30 mL Type I glass vial.
- Route of administration: intravenous (IV) infusion.
- Dose regimen: tusamitamab ravtansine loading dose at 170 mg/m² (or RD) will be administered via IV infusion over 1 hour 30 minutes on Day 1 of Cycle 1, followed by 100 mg/m² Q2W from Cycle 2 and in all other cycles.
- For participants with a body surface area (BSA) >2.2 m², the dose will be calculated based on a BSA of 2.2 m².

Noninvestigational medicinal products

Both tusamitamab ravtansine and ramucirumab have potential risk for IRR; therefore, premedication with an IV histamine H1 antagonist (diphenhydramine 50 mg IV or equivalent; eg, cetirizine, promethazine, dexchlorpheniramine, according to local approval and availability) given approximately at least 15 minutes before ramucirumab administration is required for all participants. If a participant previously experienced an IRR following a dose of ramucirumab or tusamitamab ravtansine, premedication for subsequent infusions will also include dexamethasone 10 mg IV and acetaminophen (paracetamol). All drugs used as premedication will be entered on the concomitant premedication page.

Posttrial access to study medication:

Not applicable.

Statistical considerations:

- **Analysis of primary endpoint:**
 - Incidence of DLTs during the DLT observation period (Cycle 1 and Cycle 2) will be summarized on the DLT-evaluable population, by DL (if applicable).

- Objective response rate (ORR) will be summarized on the all-treated population using descriptive statistics and 95% exact confidence intervals (CIs) will be provided using the Clopper-Pearson method. As a supplementary analysis, ORR will also be summarized on the activity population.
- **Analysis of secondary efficacy endpoints:**

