Hepatotoxicity	
Nonclinical: Following a single IV administration of tusamitamab ravtansine in mice and/or cynomolgus monkeys, increased aspartate AST, alanine ALT, ALP and/or GLDH have been noted. In addition, this was associated with mitotic arrest/single cell necrosis observed in the liver. These findings are considered related to the cytotoxic properties of DM4.
 
Clinical:
 
 In study TED13751 pooled data under hepatobiliary disorders SOC, 3 patients (1.9%) had hepatocellular injury events including 1 patient (1.3%) with Grade 4, 1 patient with a hepatic function abnormal event, and 1 patient with hypertransaminasaemia. Clinical laboratory data showed ALT increased Grade 3 in 2 patients (1.3%) and Grade 4 in 2 patients (1.3%); AST increased Grade 3 in 6 patients (3.8%) and Grade 4 in 3 patients (1.9%); ALP increased Grade 3 in 14 patients (8.9%; none with Grade 4), and blood bilirubin increased Grade 3 in 6 patients (3.8%; none with Grade 4). In study TCD15054, AST increased was reported for 1 patient (16.7%). No "Hy's law" cases have been observed. 	
Exclusion criterion (see Section 5.2).
 
Close surveillance of any signs and symptoms of hepatotoxicities.
 
Liver function tests will be performed before IMP administration at each visit. During the first 2 cycles, they will be performed on a weekly basis.
 
In case of Grade ≥ 3 liver function abnormal tests, additional tests will be repeated every 2-3 days until recovery to baseline value.

Systemic acute hypersensitivity reactions (including anaphylaxis)	
Nonclinical: Not observed.
 
Clinical:
 
 in study TED13751 pooled data, 2 patients, including 1 patient (0.6%) with Grade 3 hypersensitivity and 1 patient had Grade 1 infusion-related reaction. in study TCD15054, 1 patient (33.3%) developed rash. 	
Premedication with histamine H1 antagonist.
 
If a patient has previously experienced an infusion-related reaction in a previous tusamitamab ravtansine administration, premedication will also include dexamethasone 10 mg IV for future infusions.
 
Target infusion time is 1.5 h. In case of an IRR, the flow rate can be decreased; minimum authorized flow rate is 33 mL/h. Recommended curative action: In case of infusion reaction \geq Grade 2, tusamitamab ravtansine administration will be interrupted. The infusion may be resumed at half of the previous infusion rate after the recovery.

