Investigational medicinal products:

Ramucirumab: Ramucirumab should be administered prior to tusamitamab ravtansine infusion. Using a controlled infusion pump, ramucirumab will be administered by IV infusion over 1 hour on Day 1 of each cycle. If the first infusion is tolerated, all subsequent ramucirumab infusions may be administered over 30 minutes. In case of IRR, Grade 1 or 2, the infusion rate of ramucirumab will be reduced by 50%.

Tusamitamab ravtansine: Infusion of tusamitamab ravtansine should be initiated after the end of ramucirumab infusion. As IRRs may occur during or following ramucirumab administration, a 1 hour observation period following the ramucirumab infusion is mandatory prior the initiation of tusamitamab ravtansine administration for the first 2 infusions. If the patient shows no evidence of an IRR with the first 2 infusions of ramucirumab, no observation period is required for subsequent infusions. In the event an IRR occurs thereafter, the 1 hour observation should be reinstated.

Using a controlled infusion pump, tusamitamab ravtansine will be administered by IV infusion over 1 hour 30 minutes. For a participant with a BSA >2.2 m², the calculated dose of tusamitamab ravtansine will be based on a BSA of 2.2 m². After the first administration of tusamitamab ravtansine, participants should be observed for acute reactions on site for up to 4 hours depending on any sign of IRR. In case of a Grade 1-2 IRR, tusamitamab ravtansine must be interrupted and may be resumed only after patient recovery, at half of the previous infusion rate, with a minimum authorized flow rate at 33 mL/h. Detailed instructions for dilution and administration of the IMP is provided in Pharmacy Manual.

Noninvestigational medicinal products:

Premedication:

Both tusamitamab ravtansine and ramucirumab have potential risk of IRR; thus, premedication with an IV histamine-1 receptor antagonist (diphenhydramine 50 mg IV or equivalent; eg, cetirizine, promethazine, dexchlorpheniramine, according to local approval and availability) will be given approximately at least 15 minutes before ramucirumab administration. If a participant previously experienced an IRR following a dose of ramucirumab or tusamitamab

ravtansine, premedication will also include corticosteroids equivalent to 10 mg IV dexamethasone, and acetaminophen/paracetamol for future infusions. All drugs used as premedication will be entered on the concomitant premedication page.

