Infusion-related reactions	Grade 1-2 Mild-moderate Eg, Grade ≤ 2 nausea, headache, tachycardia, hypotension, rash, shortness of breath.	Interrupt ramucirumab infusion and start appropriate treatment. Reduce infusion rate by 50%	Interrupt tusamitamab ravtansine infusion. Tusamitamab ravtansine may be resumed only after patient recovery, at half the previous infusion rate ^a .	Give diphenhydramine 50 mg IV and/or dexamethasone 10 mg IV. ramucirumab label should be followed Dexamethasone can be added as premedication for upcoming cycles for tusamitamab ravtansine
	Grade 3-4 Severe Eg, symptomatic bronchospasm, urticaria lesions covering >30% BSA, hypotension, angioedema.	Interrupt ramucirumab infusion and definitively discontinue ramucirumab	Interrupt tusamitamab ravtansine infusion and definitively discontinue tusamitamab ravtansine and consider infusion delay.	Give diphenhydramine 50 mg IV and/or dexamethasone 10 mg IV and/or epinephrine and any required treatment per investigator judgement.
Ocular toxicity: Keratopathy/keratitis ^b associated with tusamitamab ravtansine	Grade 1 - Asymptomatic Corneal lesions only observed on routine ocular examination and not requiring topical treatment.	Administer ramucirumab at same dose, and same day as tusamitamab ravtansine	Next infusion of tusamitamab ravtansine at the same dose, with or without cycle delay, depending on the recommendation from the ophthalmologist (nature and extent of the lesion).	Standard ocular examination is planned as recommended by the ophthalmologist.

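### After an infusion reaction, Appendix 6 makes the steroid premedication that Section 6.1 requires optional, and Table 2 disagrees on when to interrupt or stop tusamitamab ravtansine

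*Protocol*

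**What the plan says.** **Premedication after a reaction.** The rule in Protocol Section 6.1 is triggered by a reaction to either drug: "If a participant previously experienced an IRR following a dose of ramucirumab or tusamitamab" ravtansine. What follows is mandatory: "premedication will also include corticosteroids equivalent to 10 mg IV dexamethasone, and acetaminophen/paracetamol for future infusions". The synopsis has the same trigger and the same force: "premedication for subsequent infusions will also include dexamethasone 10 mg IV and acetaminophen (paracetamol"). Neither text limits the rule by grade.

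The Grade 1-2 IRR row of Appendix 6 (Section 10.6, supportive care column) reads differently. For ramucirumab it says "ramucirumab label should be followed". For the other drug it says "Dexamethasone can be added as premedication for upcoming cycles for tusamitamab ravtansine". Acetaminophen is not mentioned.

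**Which text a site is sent to.** Protocol Section 8.2.7.1 names Section 6.1 for prophylactic premedication. It then directs the reader to the Appendix 6 table in the event of a hypersensitivity reaction. The SAP (Section 5.3, Premedications) also takes its definition of premedication from protocol Section 6.1.

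**Interrupting and stopping tusamitamab ravtansine.** Section 6.1 says: "In case of a Grade 1-2 IRR, tusamitamab ravtansine must be interrupted and may be resumed only after patient recovery". Appendix 6 agrees for Grade 1-2 and requires definitive discontinuation at Grade 3-4. Table 2 (Section 2.3.1, hypersensitivity row) applies its action to reactions at or above "Grade 2, tusamitamab ravtansine administration will be interrupted. The infusion may be resumed at half of the previous infusion rate after the recovery", with no upper grade stated.

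**The concern.** The extra premedication rule matters only once a participant has already reacted. At that moment Section 8.2.7.1 points the site to Appendix 6, where the steroid reads as discretionary and acetaminophen is absent. A site working from that row alone could give the next infusion without two drugs that Section 6.1 requires.

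The Table 2 mismatch concerns the reaction itself. Taken literally, Table 2 does not call for interruption at Grade 1, and it would allow an infusion to resume after a Grade 3 reaction, where Appendix 6 ends treatment with the drug.

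What is at stake is the protection of individual participants on re-exposure. The primary endpoints are not involved.

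**Working it through.** The premedication and action points are settled by comparing the texts. Only the size needs arithmetic.

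**Step 1: premedication after an IRR**

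| Source | Trigger | Force | Steroid | Acetaminophen |
|---|---|---|---|---|
| Section 6.1 | IRR to either drug, any grade | mandatory | dexamethasone 10 mg IV or equivalent | yes |
| Synopsis | IRR to either drug, any grade | mandatory | dexamethasone 10 mg IV | yes |
| Appendix 6, Grade 1-2 row | Grade 1-2 IRR | optional, for tusamitamab ravtansine | dexamethasone | not mentioned |

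Section 6.1 and the synopsis agree in substance, so the intended rule is clear and Appendix 6 is the outlier. A site that follows Section 6.1 also satisfies Appendix 6. A site that follows only Appendix 6 need not satisfy Section 6.1.

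**Step 2: action on tusamitamab ravtansine**

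| Grade | Section 6.1 | Appendix 6 | Table 2 |
|---|---|---|---|
| 1 | interrupt; resume at half rate after recovery | same | flow rate can be decreased; no interruption stated |
| 2 | interrupt; resume at half rate after recovery | same | interrupt; may resume at half rate |
| 3-4 | not addressed here | interrupt and discontinue definitively | interrupt; may resume at half rate |

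Table 2 agrees with the operational sections at Grade 2 only.

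**Step 3: how many participants**

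Inputs: one Grade 1 IRR in the TED13751 pooled data (Table 2, hypersensitivity row); 160 patients treated at 100 mg/m² every 2 weeks in that pool (Table 2, keratopathy row); up to about 38 treated participants (Section 9.1).

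- Denominator check: the hypersensitivity row prints 0.6% for a single patient. 1/160 = 0.625%, which rounds to 0.6%, so 160 fits.
- Rate: 1/160 = 0.625%.
- Exact (Clopper-Pearson) 95% CI for 1 of 160: 0.016% to 3.43%. The lower limit is 1 − 0.975^(1/160) = 0.00016. The upper limit is the value of p that solves (1−p)^160 + 160·p·(1−p)^159 = 0.025, which is p = 0.0343.
- Expected number among 38: 38 × 0.00625 = 0.24, with limits 38 × 0.00016 = 0.006 and 38 × 0.0343 = 1.30.

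The documents name IRR as a risk of ramucirumab but give no rate for it, so no count is offered for that drug.

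**The case against.** The strongest reply is that the governing text is identifiable. Section 8.2.7.1 names Section 6.1 for premedication, the SAP does the same, the synopsis agrees, and the title of Appendix 6 presents it as recommended guidance. On that view harm requires a site to read a permissive line in a guidance table as cancelling a mandatory rule stated twice. There are other safeguards too: the H1 antagonist remains mandatory for everyone, an interrupted infusion restarts at half rate, and Section 8.2.7.1 requires close monitoring with resuscitation equipment at hand. All of this stands, and it keeps the point small. It does not reconcile a mandatory instruction with an optional one on the page consulted after a reaction.

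Similarly, the permissive resumption wording in Table 2 sits in a background risk table and would not override the explicit Grade 3-4 rule in Appendix 6. That also stands, but the two should still say the same thing.

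A reader might infer more than the documents support:

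- **That there are three rival premedication rules, Table 2 being the third.** Table 2 adds dexamethasone after a tusamitamab ravtansine reaction ("in a previous tusamitamab ravtansine administration, premedication will also include dexamethasone 10 mg IV for future infusions") and is silent on ramucirumab reactions and acetaminophen. It is the risk table for tusamitamab ravtansine, so this silence is a matter of scope. Following Section 6.1 satisfies it.
- **That premedication for the continuing drug after a Grade 3-4 reaction is undefined.** Section 6.1 has no grade limit, is triggered by either drug and covers future infusions, so it already applies.
- **That the ramucirumab label conflicts with Section 6.1.** The label is not in the documents, so no conflict can be shown.
- **That the count should be 2 of 160.** The second case in Table 2 is called Grade 3 hypersensitivity and is listed apart from the IRR. The trigger in Section 6.1 is an IRR.

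**Conclusion.** The point holds in two limited parts. The Grade 1-2 IRR row of Appendix 6 is weaker than the premedication rule in Section 6.1 and the synopsis, both in force and in content. Table 2 differs from Section 6.1 and Appendix 6 on interruption at Grade 1, and from Appendix 6 on discontinuation at Grade 3-4. Both are inconsistencies between safety instructions. Section 6.1 governs premedication, and Appendix 6 gives the explicit discontinuation rule.

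The expected effect is small: about 0.24 of 38 participants with a tusamitamab ravtansine IRR (0.006 to 1.30), before asking whether any site would misread the rule. This assumes that the pooled monotherapy rate at 100 mg/m² carries over to a 170 mg/m² loading dose given with ramucirumab, which the documents do not establish. It leaves out ramucirumab reactions, for which no rate is given. Nothing here bears on the DLT or ORR analyses. The change is worth considering because it protects re-exposed participants at almost no cost.

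**What to change.** 1. **Appendix 6, Grade 1-2 IRR row, supportive care column.** Replace the optional dexamethasone sentence with: *After an IRR to either drug, premedication for future infusions will include a corticosteroid equivalent to dexamethasone 10 mg IV and acetaminophen/paracetamol, per Section 6.1.*
2. **Table 2, hypersensitivity row, mitigation column.** State: *Interrupt at Grade 1-2 and resume at half rate after recovery; discontinue definitively at Grade 3-4, per Appendix 6.* Refer to Section 6.1 for premedication.

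The cost is new wording in two table cells, which can go into the next amendment. No procedure, visit or analysis is added.

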5.2 EXCLUSION CRITERIA

Participants are excluded from the study if any of the following criteria apply:

Medical conditions

- E 01. Untreated brain metastases, leptomeningeal disease, or uncontrolled spinal cord compression. Participants with previously treated and stable brain metastases may participate. The participant must not require any systemic corticosteroids to manage brain metastases within 3 weeks prior to the first dose of study intervention.
- E 02. Significant concomitant illness, including any severe medical condition that, in the opinion of the investigator or Sponsor, would impair the participant's participation in the study or interpretation of the results.
- E 03. History within the last 3 years of an invasive malignancy other than that treated in this study, with the exception of resected/ablated basal or squamous-cell carcinoma of the skin or carcinoma in situ of the cervix, or other local tumors considered cured by local treatment.
- E 04. Known uncontrolled infection with human immunodeficiency virus (HIV). Participants with well controlled HIV infection/disease (Appendix 10; [Section 10.10](#)) must be on antiretroviral therapy (ART) to be eligible.
- E 05. Active infection with hepatitis A, B (defined as either positive HBs antigen or positive hepatitis B viral DNA test above the lower limit of detection of the assay), or C (defined as known positive result for antibodies to hepatitis C and known quantitative hepatitis C virus [HCV] RNA results greater than the lower limit of detection of the assay).
- E 06. Nonresolution of any prior treatment-related toxicity to < Grade 2 according to NCI CTCAE v5.0, with the exception of alopecia, vitiligo, or active thyroiditis controlled with hormone replacement therapy (HRT).
- E 07. Unresolved corneal disorder or any previous corneal disorder considered by an ophthalmologist to predict higher risk of drug-induced keratopathy.
- E 08. Use of contact lenses that the participant is unwilling to stop for the duration of the study intervention. The use of contact lenses is not permitted.
- E 09. Radiographic evidence of major airway or blood vessel invasion or intratumor cavitation, regardless of tumor histology.
- E 10. History of uncontrolled hereditary or acquired thrombotic disorder or history of aneurysm.

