6.5 DOSE MODIFICATION

Part 1 (Safety Run-In):

During Part 1, recommended dose of tusamitamab ravtansine in combination with ramucirumab will be determined according to the DLTs observed in participants according to the algorithm shown in [Figure 1](#).

Dose limiting toxicity definition

All AEs specified in [Table 6](#) occurring during the first 2 cycles of treatment, unless due to disease progression or to a cause obviously unrelated to IMP, will be considered DLTs. The duration of the DLT observation period will be longer for a participant who delays initiation of Cycle 2 due to a treatment-related AE for which the event's duration would determine whether the AE meets the definition of a DLT. The NCI CTCAE Version 5.0 will be used to assess the severity of AEs. Causal relationships are to be determined by the Investigator. The DLTs will be confirmed by the SC.

Table 6 - Dose-limiting toxicities

Hematological abnormalities
Grade 4 neutropenia for 7 or more consecutive days.
Grade 3 to 4 neutropenia complicated by fever (temperature $\geq 38.5^{\circ}\text{C}$ on more than 1 occasion) or microbiologically or radiographically documented infection
Grade ≥ 3 thrombocytopenia associated with clinically significant bleeding requiring clinical intervention

Nonhematological abnormalities
Grade 4 non-hematologic AE
Grade ≥ 3 keratopathy
In addition, any other AE that the recruiting Investigators and Sponsor deem to be dose limiting, regardless of its grade, may also be considered as DLT.

Abbreviations: AE = adverse event; DLT = dose-limiting toxicity.

In the case that it is decided to reduce the initial loading dose of tusamitamab ravtansine to DL -1 ([Table 1](#)), a tusamitamab ravtansine loading dose of 150 mg/m^2 will be administered to participants on Day 1 of Cycle 1.

Individual dose adjustment/dose delay: Part 1 and Part 2

Dose adjustment and/or cycle delay are permitted in case of AEs. In case of toxicity, cycle delays and dose modifications should be implemented according Appendix 6 ([Section 10.6](#)). Every effort will be made to administer the full dose regimen and maximize dose intensity.

Dose adjustments will be made according to the worst grade of AE observed within a cycle. If a participant experiences several adverse events and there are conflicting recommendations, the most conservative dose adjustment recommended should be followed.

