Any patient who has had 1 tusamitamab ravtansine dose reduction or 2 ramucirumab dose reductions and who experiences an event that would cause an additional dose reduction must be discontinued from tusamitamab ravtansine/ramucirumab.

If 1 of the 2 drugs (tusamitamab ravtansine or ramucirumab) is prematurely permanently discontinued, the other drug can be continued until disease progression.

Retreatment of a patient requiring a dose delay of more than 1 month will need to be justified by an individual case risk-benefit assessment.

6.5.1 Retreatment criteria: Part 1 and Part 2

All participants entered into the study will be treated at Day 1. A participant may receive additional study interventions if he/she meets retreatment criteria as determined by the Investigator and agrees to be retreated.

At Day 1, the participant must meet all of the following criteria to be eligible for retreatment:

- Neutrophil count $\geq 1.5 \times 10^9/L$.
- Platelets $\geq 100 \times 10^9/L$.
- Total bilirubin $\leq 1.5 \times ULN$.
- AST, ALT $\leq 2.5 \times ULN$ or $\leq 5 \times ULN$ in case of documented liver metastasis.
- No IMP-related toxicity Grade >1 (except for alopecia) or baseline severity.

- Urine protein:
 - <2+ on dipstick or urinalysis for C1D1
 - ≤2+ on dipstick or urinalysis for subsequent infusions
- OR
- <2 g on 24 hour urine collection.
- Hypertension is controlled. Every attempt should be made to control blood pressure (<150 mmHg systolic and <90 mmHg diastolic).
 - Wound healing: any wound is fully healed.

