8.2.7.10 Peripheral neuropathy

Participants with a known history of peripheral neuropathies and/or patients having received medications known to cause peripheral neuropathies (eg, prior antitubulin, platinum and/or taxanes) are at high risk of developing neuropathy. Peripheral neuropathies potentially present as signs and symptoms of sensory (paresthesia, dysesthesias, pain, and change in proprioception), motor (weakness), and neural dysfunctions.

There is no further recommendation beyond routine guidance on prevention and treatment of peripheral neuropathy. Cycle delays or modifications should be compliant with Appendix 6 ([Section 10.6](#)).

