Peripheral neuropathy	Grade 1: Asymptomatic	Administer ramucirumab as planned.	Administer tusamitamab ravtansine as planned,	Patient who has ongoing Grade 1 neuropathy has high risk of worsening of his/her symptoms and should be closely followed.
	Grade 2: Moderate symptoms; limiting instrumental Activities of Daily Living	Delay cycle until recovery to \leq Grade 1; at next cycle, administer ramucirumab the same day as tusamitamab ravtansine	Delay cycle until recovery to \leq Grade 1 and dose reduction if no improvement with dose delay	
	Grade 3: Severe symptoms; limiting self care Activities of Daily Living	Administer ramucirumab as planned.	Definitive discontinuation of tusamitamab ravtansine	
	Grade 4: Life-threatening consequences; urgent intervention indicated	Administer ramucirumab as planned.	Definitive discontinuation of tusamitamab ravtansine	
Neutrophil count decreased	Grade 1 <LLN - 1500/mm ³ ; <LLN - 1.5 × 10 ⁹ /L	No change in IMPs administration.	No change in IMPs administration	No intervention.
	Grade 2 <1500 - 1000/mm ³ ; <1.5 - 1.0 × 10 ⁹ /L	Delay the cycle until recovery of absolute neutrophil count >1500/mm ³ . Restart at the same dose.	Delay the cycle until recovery of absolute neutrophil count >1500/mm ³ . Restart at the same dose.	No intervention.
	Grade 3 <1000 - 500/mm ³ ; <1.0 - 0.5 × 10 ⁹ /L Or	Delay the cycle until recovery of absolute neutrophil count >1500/mm ³ . Restart when absolute neutrophil count >1500/mm ³ at the same dose. Prophylactic G-CSF can be considered in all subsequent cycles	Delay the cycle. Restart the treatment when absolute neutrophil count >1500/mm ³ at the same dose; prophylactic G-CSF can be considered in all subsequent cycles	Follow ASCO guidelines on usage of G-CSF and antibiotherapy (13). Repeat test every 3 days.
	Grade 4 <500/mm ³ ; <0.5 × 10 ⁹ /L			

Event	Symptoms severity (Nadir) (NCI CTCAE v5)	Management of IMP dosing (ramucirumab)	Management of IMP dosing (tusamitamab ravtansine)	Supportive care guidelines

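### For IMP-related Grade 2 peripheral neuropathy that does not improve with delay, Appendix 6 most naturally allows a reduced dose, Section 6.5.1 bars retreatment above Grade 1 or baseline severity, and nothing says which prevails

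*Protocol*

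**What the plan says.** Three pieces of Protocol text govern a participant with IMP-related Grade 2 neuropathy.

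- **Appendix 6 (Section 10.6), Peripheral neuropathy, Grade 2, tusamitamab ravtansine column.** The cell opens with "Delay cycle until recovery to" Grade 1 or lower and continues "and dose reduction if no improvement with dose delay".
- **Same row, ramucirumab column.** The cycle is likewise delayed to Grade 1 or lower, and then "at next cycle, administer ramucirumab the same day as tusamitamab ravtansine". Nothing is said about a delay that brings no improvement.
- **Section 6.5.1, for Part 1 and Part 2.** "At Day 1, the participant must meet all of the following criteria to be eligible for retreatment". One criterion reads "No IMP-related toxicity Grade >1 (except for alopecia) or baseline severity". Alopecia is the only named exemption.

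Two other sections send the site to Appendix 6. Section 6.5 says "In case of toxicity, cycle delays and dose modifications should be implemented according Appendix 6", and Section 8.2.7.10, on neuropathy, says "Cycle delays or modifications should be compliant with Appendix 6". Neither mentions Section 6.5.1.

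**The concern.** A participant who has not improved with delay is still at Grade 2. If the second half of the Appendix 6 cell is an instruction for that participant, it directs a reduced dose at a grade for which Section 6.5.1 refuses retreatment. The cell also sits awkwardly with its own first half, which holds the cycle until Grade 1 or lower.

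Peripheral neuropathy is an identified risk of tusamitamab ravtansine (Section 2.3.1), and Section 8.2.7.10 counts prior platinum among the exposures that put participants at high risk. Inclusion criterion I 05 admits participants after platinum and/or fluoropyrimidine. The choice between passages also has a later effect. Table 7 permits one tusamitamab ravtansine reduction, and Section 6.5 requires discontinuation if a further reduction would be needed. A site that uses the Appendix 6 branch spends that single reduction, while a site that follows Section 6.5.1 goes on holding. Two similar participants could then have different exposure and different reasons for stopping, depending only on which page the site consulted.

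**Working it through.** The plan states no figure on this point, so the check is mainly a comparison of texts.

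**Step 1. One worked case under each rule.** Take a participant with no neuropathy or Grade 1 at baseline, who develops IMP-related Grade 2 neuropathy and remains at Grade 2 after a delay.

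| Text | Result on Day 1 of the next cycle |
|---|---|
| Appendix 6, tusamitamab ravtansine, first half | Keep delaying |
| Appendix 6, tusamitamab ravtansine, second half, natural reading | Give a reduced dose |
| Appendix 6, ramucirumab | Keep delaying; no branch if the other drug is given |
| Section 6.5.1 | Not eligible for retreatment |

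**Step 2. Does the baseline-severity exception remove the conflict?** Rarely. Exclusion criterion E 06 keeps out participants with "Nonresolution of any prior treatment-related toxicity to < Grade 2 according to NCI CTCAE v5.0" (alopecia, vitiligo and controlled thyroiditis apart). The exception could therefore matter only for Grade 2 neuropathy at baseline that was not caused by earlier treatment.

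**Step 3. Does any other provision settle it?**

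- The Section 6.5 rule to take the most conservative adjustment is written for several adverse events with conflicting recommendations, not for one event under two sections.
- The Section 6.5 rule on delays of more than 1 month asks for an individual risk-benefit assessment. It does not waive the Grade 1 criterion.
- The Section 6.5 requirement to consult the sponsor covers departures from the protocol. Here both actions are in the protocol.
- Table 2 names delay or reduction for neuropathy, and discontinuation for Grade 3-4, without saying what happens when Grade 2 persists.

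**Step 4. How many participants?** The documents do not report Grade 2 neuropathy, or its persistence after delay. The following only sets bounds.

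- Any-grade rate at 100 mg/m² Q2W: 43 patients (Table 2, neuropathy row) of 160 (Table 2, keratopathy row). 43/160 = 26.9%, as printed. Scaled to 32 participants: 0.269 × 32 = 8.6.
- Assume that one quarter to one half reach Grade 2: 8.6 × 0.25 = 2.2 and 8.6 × 0.5 = 4.3, or about 2 to 4. This share has no source in the documents.
- At this trial's loading-dose regimen, Section 2.3.1 reports peripheral sensory neuropathy in 2 of 13: 2/13 × 32 = 4.9 at any grade. The same share gives 1.2 to 2.5.
- In the 16-participant gastric cohort, no neuropathy term appears among events reported in more than 10%. Any single term therefore occurred in at most 1 of 16: 1/16 × 32 = 2 at any grade. The same share gives 0.5 to 1.

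The last two rates are for single preferred terms and are not strictly comparable with the 26.9%. All three results count participants who reach Grade 2. Those who then fail to improve with delay are a subset of unknown size.

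**The case against.** The best counter-argument is that the cell can be read without conflict: delay until Grade 1 or lower and, if the delay went poorly, restart at a reduced dose once that grade is reached. The Grade 2 keratopathy row, second episode, has a similar form, with recovery as the gate and reduction as the dose at restart. On this reading Section 6.5.1 decides whether to dose and Appendix 6 decides how much. Appendix 6 is also titled as recommended guidelines, while Section 6.5.1 is worded as a requirement.

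This stands in part. A reader might infer a flat contradiction, and the documents do not support that, because the harmonising reading exists. It is strained, however. The keratopathy reduction depends on the episode number, and the rows for prolonged Grade 4 neutropenia and proteinuria likewise state recovery first and the reduced dose second. Only the neuropathy cell makes the reduction depend on a lack of improvement. The difference in wording strength is not stated as an order of precedence.

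It is also fair to say that persistent toxicity is not left wholly unmanaged. Section 6.5 discontinues treatment for an event that persists despite appropriate dose modifications, and long delays get individual review. These provisions limit how long the ambiguity can last for one participant, but they do not say which instruction applies at the first visit where Grade 2 persists.

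**Conclusion.** The concern holds as an unresolved inconsistency in safety management. On the most natural reading of Appendix 6, the same participant could be given a reduced dose of tusamitamab ravtansine or be withheld under Section 6.5.1. No passage states which prevails, and the handling of ramucirumab in that situation is not defined.

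Three stronger inferences are not supported:

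- **That Section 6.5.1 forbids all dosing above Grade 1.** It covers IMP-related toxicity only and allows baseline severity.
- **That 2 to 4 of 32 participants fall under the conflict.** That range counts every Grade 2 case, rests on an assumed Grade 2 share and uses the highest of the available rates. It is an upper figure. Prior taxane is excluded here (E 21), which may lower the risk further, although prior platinum remains. The affected number is probably few and may be none.
- **That the primary efficacy result is at risk.** The trial tests no hypothesis, and objective response is assessed regardless of study intervention discontinuation (SAP Section 3.2.2.1).

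What can move is descriptive: dose delay, reduction and relative dose intensity (SAP Sections 3.6.1.2 and 3.6.1.3), adverse events leading to dose modification or discontinuation (SAP Table 8), and neuropathy events (SAP Table 9). With about 32 participants, even a few site-dependent decisions would be visible there. The point merits correction mainly because it concerns consistent handling of an identified risk.

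**What to change.** The sponsor must reconcile the Grade 2 peripheral neuropathy row of Appendix 6, in both drug columns, with Section 6.5.1, so that a single instruction applies when Grade 2 neuropathy persists after a delay. The revised text should make explicit whether the reduction in the Appendix 6 cell applies before or only after recovery, and what is done with ramucirumab in the same situation. Which rule applies is a clinical decision for the sponsor, and none is proposed here.

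The cost is a short protocol clarification through the usual amendment approval (Section 10.1.1). Sample size and analysis do not change.
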